## 1.0 Objectives / Specific Aims

The goal of this project is to establish the safety, feasibility, and acceptability of abbreviating and accelerating telehealth-delivered imaginal exposure therapy for post-traumatic stress disorder (PTSD). Importantly, conventional telehealth-delivered Prolonged Exposure (PE) therapy is non-inferior to the conventional, gold standard in-person PE for PTSD (Acierno et al., 2017). Intensive or massed schedules of in-person exposure- based trauma-focused treatments have likewise recently been shown, in a nascent but promising literature, to produce comparable treatment outcomes to conventional once or twice weekly schedules, but importantly, with lower levels of premature dropout (Sciarrino et al., 2020; Zoellner et al., 2017).

**AIM 1: Establish the safety of VVC-delivered massed imaginal exposure for PTSD.** We hypothesize that VVC-delivered, massed imaginal exposure will be safe as indexed by no significant adverse events.

**AIM 2: Establish the feasibility, tolerability, and acceptability of VVC-delivered massed imaginal exposure for PTSD.** We hypothesize that 1) veterans will consider the treatment acceptable and tolerable and that 2) recruitment and retention will be feasible (> 80% retention).

**EXPLORATORY AIM 1: Establish acceptability among stakeholder providers of VVC-delivered massed imaginal exposure for PTSD.** We hypothesize that 1) telemental healthcare providers will consider the treatment acceptable and tolerable and that 2) will be willing to receive training and/or refer patients to such services.

**EXPLORATORY AIM 2: Establish the preliminary efficacy of VVC-delivered massed imaginal exposure for PTSD.** We hypothesize that 1) veterans will demonstrate moderate reductions in posttraumatic stress and associated symptoms and impairment from intake to the end of treatment that will in turn, 2) be maintained or extended at the 1-month post-treatment follow-up.

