## 2.0 Background

**The need for enhancing PTSD treatment.** PTSD is a chronic, impairing condition with variable rates of recovery. PE, which consists primarily of imaginal and in vivo forms of exposure to trauma reminders, is an effective first-line intervention (Power et al., 2010), with wide acceptance among evidence-based practitioners. However, many PTSD patients show non- remittance (~25-50%; Rosellini et al., 2018), poor treatment responses (~60%); Loerinc et al., 2015) and dropout (~18-68%; Imel et al. 2013). Thus, there are well-defined needs to improve the efficacy, effectiveness, efficiency, and tolerability of this challenging, but potent form of intervention, and an equally pressing need to develop and deploy technologies that enhance access to treatment.

**Accelerated protocols for enhancing treatment efficacy and efficiency.** In response to calls to enhance the efficiency of exposure-based treatments, accelerated protocols have been demonstrated to be non-inferior to the standard PE protocol. This includes a previous trial by Col [name] and colleagues that implemented a daily 6-session protocol (Zoellner et al., 2017), resulting in comparable efficacy and much lower dropout (6.3%) compared to standard bi-

weekly 10-session PE. This is consistent with a small, but growing number of studies of massed evidence-based treatments for PTSD, which have revealed large effects ( $d = 1.15\text{--}2.93$ ) and low attrition across studies (5.1%; Sciarrino et al., 2020). Thus, by reducing burden by enhancing efficiency, accelerated protocols may especially be indicated for those at high risk of dropout, such as Veterans (28.1%; Eftekhari et al., 2013).

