## 10.0 Data Management

**Data Acquisition.** If (and only if) ultimately approved by the VA, we propose the use of VA Qualtrics, which is a secure, FedRAMP-authorized online data capture system that is widely used as a HIPPA-compliant web-based means to collect sensitive research data. Moreover, if approved, in addition to remotely collecting validated self-report questionnaire data from participants using this platform, we also request leveraging Qualtrics' functionality to integrate java script, which would enable us to directly capture audio and visual data from the participant's side from their webcam and microphone. This is an excellent alternative to our initially proposed procedures, which involve collecting streamed, then captured (i.e., on the clinician's side) footage. This is problematic due to significant temporal distortion and low sampling rate for screen-captured footage on currently deployed telehealth platforms approved by the VA (i.e., Teams, Webex, and VVC). As mentioned, the use of Qualtrics will be entirely contingent on obtaining full MUSC IRB and VA R&D approval for our proposed use. If ultimately not approved, we will continue to implement our procedures that involve capturing questionnaire data with hard copies, by mail.

**Data Preparation.** Pre-processing of data as the study progresses will allow for more expedient dissemination of study findings. As appropriate, pre-processing will follow standard best practices to ensure excellent data quality and security. Prior to analyses, data will be visually and statistically inspected for the presence of aberrant data points, which will be omitted prior to analyses.

**Analytical Plan.** Descriptive statistics will be reported for safety, feasibility, tolerability, and acceptability. Linear mixed-effects models will be used to characterize trajectories of change in symptoms and impairment, while controlling for potential confounders, such as baseline severity.

Following standard pre-processing steps, analyses will be conducted using generalized linear models, and will proceed in a bottom-up manner involving selection of the best fitting fixed and random growth terms, followed by adding predictors of interest. Factors (e.g., sex) will be dichotomously coded, whereas all continuous predictors will be scaled and centered as a function of baseline values to allow for meaningful interpretation of effects as indicative of reliable change.

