Additionally, all models will control for baseline levels of the outcome to control for individual differences at pre-treatment in estimating effects. Model refinement will be guided by theory, evaluating standard fit statistics (e.g. Log Likelihood, AIC, BIC, etc.) and whether modeling assumptions are sufficiently met.

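### Scaling predictors by baseline values cannot make model effects show reliable change, and no reliability or individual threshold is specified

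*Combined protocol and SAP*

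**What the plan says.** The combined protocol and SAP deals with this in Section 10.0, Analytical Plan. The main efficacy tool is stated as "Linear mixed-effects models will be used to characterize trajectories of change in symptoms and impairment". Growth terms are selected first and predictors of interest are added afterwards. Categorical factors are coded as two-level variables, while every continuous predictor is to be "scaled and centered as a function of baseline values to allow for meaningful interpretation of effects as indicative of reliable change". The same section adds that "all models will control for baseline levels of the outcome".

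The scaling function is not defined, and no scaling of the outcomes is mentioned. Neither Section 10.0 nor the descriptions of the measures in Section 9.0 give a reliability coefficient, a standard error of measurement, a reliable-change index or a rule for classifying individual participants.

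The analysis serves Exploratory Aim 2 (Section 1.0), which hypothesises "moderate reductions in posttraumatic stress and associated symptoms and impairment from intake to the end of treatment" without putting a number on it. Section 2.0 acknowledges that the study lacks power for efficacy and says that its effect estimates will help to plan later randomised trials. CAPS-5 and PCL-5 are nevertheless listed under Primary Outcome Measures in Section 9.0.

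**The concern.** In its established sense, reliable change is a statement about one person: did that person's score move further than the scale's measurement error would explain? The plan attaches the term to regression coefficients and gives a change of units as the justification. A report that follows this sentence could present a significant average effect as reliable change, and readers could take that to mean that individual veterans reliably improved. The estimates are meant to inform later trials and two of the scales carry the primary label, so the wording matters beyond style. It does not affect the primary descriptive questions of safety, feasibility and acceptability.

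**Working it through.** **Inputs from the document.** 25 enrolled, 20 expected to complete, 20% allowance (Section 4.0). Massed-treatment literature d = 1.15 to 2.93 (Section 2.0).

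**Assumptions, because the document gives no values.** Reliability r = 0.70 to 0.95; pre-post correlation ρ = 0.3 to 0.7; a moderate effect = 0.5 baseline SD; two-sided 5% level; equal variances before and after treatment; normally distributed changes.

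**Step 1. The plan's own figure.** No figure is given for reliable change. The sample-size figure reproduces: 20 / (1 − 0.20) = 25. I use n = 20 below.

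**Step 2. What the scaling does.** Take y = a + b·x and replace x by z = (x − m)/s. Then y = (a + b·m) + (b·s)·z. Fitted values, residuals and the test of the slope are unchanged. The new coefficient b·s is in raw outcome units per s units of the predictor. It is not a change in baseline SD units of the outcome, and no reliability enters. The random growth terms describe spread between participants, but no criterion is set for classifying anyone.

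**Step 3. What an individual reliable-change threshold requires.** In baseline SD units it is 1.96 × √(2(1 − r)):

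| Assumed r | Threshold (baseline SD) |
|---|---|
| 0.70 | 1.96 × √0.60 = 1.52 |
| 0.80 | 1.96 × √0.40 = 1.24 |
| 0.85 | 1.96 × √0.30 = 1.07 |
| 0.90 | 1.96 × √0.20 = 0.88 |
| 0.95 | 1.96 × √0.10 = 0.62 |

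**Step 4. How small a mean change could be significant.** A paired comparison serves as a simple stand-in for the mixed model. With n = 20 the smallest significant mean change is t(0.975, 19) × √(2(1 − ρ)) / √20. This gives 0.55 SD at ρ = 0.3, 0.47 at ρ = 0.5 and 0.36 at ρ = 0.7.

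**Step 5. How many individuals would pass at a mean change of 0.5 SD.** The share is 1 − Φ[(threshold − 0.5) / √(2(1 − ρ))]. At r = 0.90 and ρ = 0.5 it is 1 − Φ[(0.877 − 0.5)/1] = 35%. Over r = 0.70 to 0.95 and ρ = 0.3 to 0.7 it runs from about 9% to 46%. So 54% to 91% would not show an improvement beyond their own threshold.

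**Step 6. Measurement error in the mean.** Averaging over n = 20 divides the individual bound by √20: 0.877 / 4.472 = 0.20 SD at r = 0.90, and 1.518 / 4.472 = 0.34 SD at r = 0.70. A mean change of 0.5 SD lies beyond what measurement error alone would produce.

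Steps 5 and 6 answer different questions. The same mean change can be clearly distinguishable from measurement error as an average and still leave most participants short of reliable improvement. The plan's sentence merges the two.

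**The case against.** The strongest reply is that this is a loose phrase in an exploratory analysis. The plan names no reliable-change index, sets no cut-off and contains no rule that effects will be reported as reliable. Because the scaling function is undefined, it could in principle include a measurement-error term. All the reliabilities above are assumed, as is 0.5 SD for a moderate effect. The literature that the plan cites points to something larger: "which have revealed large effects", with d from 1.15. If that d is in baseline SD units, it exceeds the individual threshold at r = 0.85 and above, though not at 0.80 and below. A count of individual responders is also an analysis that no stated aim calls for.

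Most of this stands, and it limits the point. Three stronger readings are tempting and should be resisted:

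- A reader might infer that the plan ignores measurement error. It only fails to specify any such term.
- A reader might infer that group effects below 0.62 to 1.24 SD will be reported as reliable. The text states an intended interpretation, not a reporting rule, so this could happen but is not planned.
- A reader might infer that a group effect below the individual threshold is unreliable. Step 6 shows otherwise, and applying the individual threshold to a mean would repeat the confusion of levels.

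The reply does not rescue the stated inference. Whatever baseline function is used to rescale the predictors, Step 2 applies: the units change, and the outcome and the level of inference do not.

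**Conclusion.** The point holds in a narrow form. The plan attributes to its model effects a property that the described step cannot give them, and it supplies none of the quantities needed to claim that property. The possible consequence is a description of an average effect that readers take as a statement about individuals. Under the assumptions above, a mean change of 0.36 to 0.55 SD could be significant with 20 completers, while at 0.5 SD fewer than half of participants would pass their own threshold. These figures are illustrative and would shift with the actual reliabilities, and effects as large as those cited would narrow the gap. The point is minor: the efficacy aim is exploratory, and deleting the phrase changes no sample size, model or test.

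**What to change.** Delete the reliable-change clause from the Analytical Plan. State that model effects will be reported in scale points and in baseline SD units of the outcome, with confidence intervals.

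Separately, for CAPS-5 and PCL-5, report the number and percentage of participants whose own change exceeds 1.96 × baseline SD × √(2(1 − r)). Do this in each direction, from pre-treatment to post-treatment and from pre-treatment to the 1-month follow-up, with exact 95% confidence intervals. State the value and source of r for each scale before the data are analysed, and give the denominator at each time point.

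No new data collection is needed, because the assessment schedule in Section 9.0 has both scales at all three assessments. The cost is one additional table, the work of choosing and citing a reliability for each scale, and a claim likely to be less favourable than the present wording invites.

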## **11.0 Provisions to Monitor the Data to Ensure the Safety of Subjects**

Safety will be monitored by reports of adverse events at all study visits throughout all phases of the project. This will include formal assessment of psychiatric symptoms (including suicidality and homicidality) as well as invitation at each study visit to speak to a therapist regarding any suicidal or homicidal thoughts and a reminder about the Veterans' Crisis Line. Formal assessment of suicidality will be conducted using the C-SSRS, and suicidality will also be monitored throughout study participation based on item 9 on the PHQ-9. Should a Veteran endorse suicidality on this question, or otherwise report to study staff any thoughts of wanting to hurt him/herself or others, the veteran will be fully evaluated for safety, and steps to ensure safety will be followed. Suicidal or homicidal plan or intent will be immediately reported to the PI.

All research participants will be assigned a numeric code (Subject ID) that is based on the chronological order in which they were enrolled in the study. This number accompanies all de-identified data. The participant's identifying information and numeric code will be stored in the password-protected database on a protected VA virtual drive previously described. Password to participant data will be updated quarterly as an additional security measure. All identifying information (e.g., signed consent forms and contact information) will be maintained separately from the rest of the study data collected. The Subject ID will not contain any identifiers or protected health information (PHI) as defined by HIPAA. All data on separate VA data analysis computers (that are also password protected) are stripped of potential identifiers, with special attention paid to the problem of "cell size." VA research data will be retained according to RCS 10-1 and VA Information Security policies. Moreover, if the proposed use of Qualtrics is ultimately approved, all procedures described above to de-identify

data will apply. Specifically, data will only be connected to a numeric code (i.e., Subject ID, last name initial, and last four of SS#).

Upon study completion, all links between identifiers and clinical research data will be deleted. The process for de-identifying data will be completed by a qualified biostatistician with an extensive background in statistics, mathematics, clinical science, and knowledge of and experience with generally accepted statistical and scientific principles and methods for de-identification applying generally accepted principles and methods, as outlined in VHA DIRECTIVE 1605.01, Appendix A.

In addition, for participants who express willingness to be contacted for future research opportunities on their informed consent document, we will retain their contact information (i.e., name, address, and phone number) in a repository consisting of a password-protected spreadsheet, with the password updated quarterly. These data will likewise be stored on a secure VA server.

**Data and Safety Monitoring Plan (DSMP).** The PI, [name] will be in charge of (1) providing scientific oversight; (2) reviewing all adverse effects or complications related to the study; (3) monitoring enrollment; (4) reviewing summary reports relating to compliance with protocol requirements; and (5) providing advice on resource allocation. [name] will meet every 6-months in-person and as necessary with the Col-s as an internal Data Safety Monitoring Committee (DSMC) to review progress. The recommendations of the DSMC will be reviewed and the PI will take appropriate corrective actions as needed. At each meeting the DSMC will:

- Review the research protocol and plans for data and safety monitoring.
- Evaluate the progress of the study, including periodic assessments of data quality and timeliness, participant recruitment, enrollment, and retention, participant risk versus benefit, integrity of the intervention, and other factors that can affect study outcome.
- Consider factors external to the study when interpreting the data, such as scientific developments that may impact the safety of study participants or the ethics of the study.
- Make recommendations to the IRB for continuation or termination of the study.
- Protect the confidentiality of study data and monitoring.

DSMC reviews and reports will occur on a semi-annual basis and will be organized and prepared by the PI. Planned interim analysis will occur once 50% of the target study enrollment is reached ( $N = 13$ ).

On a daily basis, [name] will be responsible for data and safety monitoring and will provide continuous, close data monitoring. [name] will promptly report serious adverse events to the MUSC Institutional Review Board (IRB). A report of all non- serious adverse events will be provided to the IRB yearly.

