#### 4.0 Inclusion and Exclusion Criteria/ Study Population

Veterans who are aged 18-65 (inclusive), who meet full DSM-5 criteria for current PTSD will be recruited from all racial, ethnic and gender categories. The rationale regarding a cutoff of 65 years was for correspondence to prior massed in-person protocols (e.g., Zoellner et al, 2017). Planned follow up studies will include a broader age range and will be powered to analyze age effects on outcomes. To contend with dropout, we propose to enroll 25 veterans, with the aim of completing assessments and treatment for 20 participants. In-person investigations have shown a dropout rate of 5% (Sciarrino et al. 2020), thus a 20% allowance will ensure adequate recruitment to meet study aims.

**Exclusion Criteria.** Participants will be excluded for the following: 1. clinically unstable physical illness; 2. bipolar Type I disorder; 3. dementia; 4. repeated abuse or dependence upon drugs within 3 months; 5. unstable psychotropic regimen within 6-weeks; and finally, 6. active suicidal ideation or a suicide attempt within the past year.

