## 8.0 Consent Process

All participants will be referred on the basis of a routine intake assessment in the PCT or another VA behavioral health clinic prior to study entry. As indicated above in the eligibility criteria, those who report clinical symptoms that suggest trauma-focused therapy for PTSD is not in their best interests will be excluded from the study and directed to alternate care as recommended by the PCT and their clinical care team. Participants who appear to meet criteria for entry into the study will be informed of the study and if they express interest, they will review

study consent, and HIPAA Authorization with study personnel (PI, study coordinator, or study evaluator).

The consent process and HIPPA authorization procedures will be completed electronically through VVC or another VA-approved videoconferencing platform, following all VA institutional guidelines pertaining to the consent and authorization procedures. Consent documents will be provided by mail, or through secure messaging, then subsequently reviewed with study personnel at the first study visit (i.e., the pre-treatment or baseline assessment). During review of consent, study staff will detail study procedures and ensure that patients understand what components are part of the study procedures and what is part of standard treatment for PTSD. Study staff will ensure that potential participants understand the study and are interested and able to complete study procedures prior to providing signed informed consent. Participants will receive in the consent document emergency contact information for use in case of acute exacerbation of symptoms. Participants will be informed that they can withdraw from the study at any time and receive alternate care outside of the study. Participants will also be informed that if they report imminent suicidality or intolerance for study procedures at any point during the protocol, they may be withdrawn from the study and receive alternate care as appropriate (i.e., inpatient hospitalization, treatment in outpatient psychiatry, etc.).

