### Primary Outcome Measures

**Treatment Dropout/Completion.** We will collect data on treatment completion, to include the number of treatment sessions and assessment visits attended, via chart review from CPRS.

**Treatment Non-Compliance.** We will collect data on treatment compliance, including completion of in-session and between-session assignments, as determined by chart review and self-report.

**Satisfaction with Therapy and Therapist Scale - Revised (STTS-R).** The STTS-R is a 13-item Likert-type self-report scale designed to assess patient satisfaction with therapeutic services and providers (Oei & Green, 2008). This instrument will be administered at the post-treatment and 1-month follow-up time-points.

**Technology and Treatment Satisfaction Questionnaire (TTSQ).** The TTSQ is a 14-item self-report measure developed by the investigators. Items assess satisfaction, acceptance, tolerability, perceived utility and treatment outcome-related expectancies related to incorporating the remote affective physiology procedures into the assessment procedures (see below), as well as opinions about incorporating such measures into routine care. Both patients and

providers will complete slightly different versions of this measure, addressing the same items, but adapted appropriately for wording. This instrument will be administered at the post-treatment time-point.

**Clinician-Administered PTSD Scale for DSM-5 (CAPS-5).** The CAPS-5 is a structured interview for diagnosis of PTSD and is widely considered the gold-standard assessment (Blake et al., 1995; F. W. Weathers et al., 2018). The CAPS-5 will be administered at pre-treatment, post-treatment, and the 1-month follow-up visits, and will be used to evaluate inclusion criteria and as a comparative criterion to assess relations between our objective measurements and severity of trauma-related symptoms and functional impairments.

**PTSD Symptom Checklist for DSM-5 (PCL-5).** The PCL-5 is a 20-item self-report measure of PTSD symptom severity based on the DSM-5 (Wortmann et al., 2016). This measure will be administered at pre-treatment, post-treatment, and the 1-month follow-up, serving as a primary self-report outcome measure. It will also be administered at the beginning of each treatment session, to index trajectories of change over the course of treatment.

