## **12.0 Withdrawal of Subjects (if applicable)**

If it is determined that it is not in the subject's best interest to continue participating in the study, he or she will be withdrawn from the study without their consent. Examples of such circumstances include emergence of symptoms or

behavior that meet study exclusion criteria, consistent non-compliance with study assessment instructions, or if treatment of other acute health/mental health symptoms becomes a priority over study participation. In such cases, the PI will meet directly with the subject to explain the reasons for withdrawal from the study, and to assess whether any further action is required, including additional mental health intervention or modification of the current treatment plan. The treating therapist will be included in this discussion as appropriate.

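### No adverse event source, observation window or denominator is specified once a Veteran stops treatment or is withdrawn, and any later event missed can only favour Aim 1

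*Combined protocol and SAP*

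**What the plan says.** Section 1.0 states the Aim 1 hypothesis: "massed imaginal exposure will be safe as indexed by no significant adverse events". It does not define a significant event, the period over which events count, or the group over which they are counted. Section 10.0 (Analytical Plan) says safety will be summarised descriptively.

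On collection, section 11.0 says: "Safety will be monitored by reports of adverse events at all study visits throughout all phases of the project". It adds suicidality monitoring by the C-SSRS and by PHQ-9 item 9 during participation. In the section 9.0 schedule the C-SSRS after baseline falls only at the post-treatment and 1-month visits, and section 6.0 times the post-treatment visit from completing treatment.

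On leaving, section 8.0 tells Veterans that "if they report imminent suicidality or intolerance for study procedures at any point during the protocol, they may be withdrawn from the study", with alternate care that may include hospital admission. Section 12.0 covers a Veteran for whom staying in is judged not to be in his or her interest: "he or she will be withdrawn from the study without their consent". Its examples include newly emerging exclusion criteria and acute symptoms that take priority over the study. Section 12.0 describes one meeting with the PI at that point.

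On numbers, section 4.0 says: "we propose to enroll 25 veterans, with the aim of completing assessments and treatment for 20 participants".

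The chart is already in use. Section 9.0 (Primary Outcome Measures) collects session and visit attendance "via chart review from CPRS" and uses chart review, with self-report, for compliance. Table 1 in section 4.0 uses it for some exclusions. Adverse events are not mentioned in either place.

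**The concern.** The plan's own rules link leaving the study to safety: suicidality, intolerance and acute symptoms are grounds for withdrawal. The stated collection of adverse events is tied to visits, and no visit timing is defined for someone who stops early. If such a Veteran is admitted to hospital two weeks after leaving, the plan does not say whether anyone would record it or whether it would count in Aim 1. In a descriptive count, a person with no later data looks the same as a person with no later event.

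This error runs in one direction. Events missed after exit cannot raise the count, so they can only help a hypothesis that is supported by finding none. At stake is whether a result of no significant adverse events in this pilot can be read as applying to all Veterans who began treatment or only to those who stayed.

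**Working it through.** **Step 1. The plan's own figure.** Section 4.0 enrols 25 to obtain 20 completers with a 20% allowance: 20 / (1 − 0.20) = 25. This reproduces, so the plan itself budgets for 5 of 25 Veterans with incomplete treatment or assessment. For comparison, the 5% dropout that section 4.0 cites for in-person studies is about 1 of 25 (25 × 0.05 = 1.25), and the 28.1% that section 2.0 cites for Veterans is about 7 of 25 (25 × 0.281 = 7.0).

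**Step 2. Which contacts could carry an event report, and whether they continue after exit.**

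| Contact | Where | Described as adverse event collection? | Stated to continue after exit? |
|---|---|---|---|
| Reports at study visits | 11.0 | Yes | No |
| Nightly provider check-in | 9.0, Treatment Procedures | No | No |
| Spontaneous report to staff of thoughts of harm | 11.0 | No; it triggers a safety evaluation | Not stated |
| PI's daily safety monitoring and reporting of serious events | 11.0 | Yes, but no data source is named for people who have left | Not stated |
| PI meeting at withdrawal | 12.0 | No | One meeting |
| Re-evaluation and treatment of those at elevated suicide risk | 13.0 | No; it is clinical care | Duration not stated |

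No row supplies a specified source of adverse events after exit.

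**Step 3. Effect on the chance of recording no event.** The documents give no event rates, so the risks are assumptions. Let p be the event risk in each of 20 completers, and q the risk in the unobserved period of each of 5 non-completers.

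- Recorded, with the 5 unobserved: (1 − p)^20
- Full capture: (1 − p)^20 × (1 − q)^5

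| p | q | Recorded | Full capture | Difference (points) |
|---|---|---|---|---|
| 2% | 2% | 66.8% | 60.3% | 6.4 |
| 2% | 6% | 66.8% | 49.0% | 17.8 |
| 2% | 10% | 66.8% | 39.4% | 27.3 |
| 5% | 5% | 35.8% | 27.7% | 8.1 |
| 5% | 15% | 35.8% | 15.9% | 19.9 |
| 5% | 25% | 35.8% | 8.5% | 27.3 |
| 10% | 10% | 12.2% | 7.2% | 5.0 |
| 10% | 30% | 12.2% | 2.0% | 10.1 |

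Differences are taken before rounding. Worked row: 0.98^20 = 0.668, 0.90^5 = 0.590, and 0.668 × 0.590 = 0.394.

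Over these pairs, in which q runs from equal to p up to five times p, the chance of a no-event result rises by about 5 to 27 points. For the risks shown this is an upper limit. Events that non-completers have before exit would be recorded either way. If s is that earlier risk, both columns are multiplied by (1 − s)^5, which is at most 1, so the difference shrinks. It shrinks again if some of the 5 still attend the assessments.

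**Step 4. What a count of zero would support.** The exact one-sided 95% upper bound with no events in n people is 1 − 0.05^(1/n). For n = 25 followed it is 11.3%; for n = 20 it is 13.9%. If 5 are not followed and each is counted as a possible event, the worst case is 5/25 = 20%. Without a stated denominator and a count of those not followed, a reader cannot tell which of these applies.

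**The case against.** The strongest reply is that these Veterans are not simply lost from view. Nightly check-ins run during treatment, staff act on spontaneous reports, the PI monitors safety daily and meets anyone withdrawn by the study, and section 13.0 has the PI and a co-investigator re-evaluate and treat those at elevated suicide risk with the care team. This stands. A reader might infer that events are found only through study visits, and the documents do not support that. They do not, however, describe any of these contacts as adverse event collection that continues after exit.

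Stopping treatment is also not the same as leaving the study. Section 9.0 counts sessions and assessment visits separately, and nothing says that a Veteran who stops therapy loses the 1-week and 1-month assessments. A reader might infer that dropouts receive no follow-up; what can be said is that none is specified.

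The report of suicidality or intolerance that leads to withdrawal comes before exit and would be known. What remains open is later events, and how the triggering event is counted.

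A reader might also assume a far higher risk in those who leave, say 20–50%, with none of their events captured, and obtain a much larger effect. The documents give no event rates by dropout status, and section 2.0 links dropout partly to treatment burden. Higher risk in leavers is plausible but not shown.

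Finally, this is a 25-person descriptive pilot. That limits how much the point weighs, but safety is its first aim.

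**Conclusion.** The concern holds in a limited form. The plan's systematic source of adverse events is tied to visits, and it specifies no source, window or denominator after a Veteran stops or is withdrawn, although some withdrawals are themselves for safety reasons. Later events may be missed; whether they would be depends on practice that the plan does not describe. The direction is certain: missed events can only favour the Aim 1 hypothesis. The size is not. With 5 of 25 unobserved and the assumed risks above, the chance of a no-event result rises by at most about 5 to 27 points. It would be less with fewer Veterans unobserved, and more if their risk were higher than assumed. The plan should be changed on this point, because a better source is already being opened for other purposes.

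**What to change.** Add to section 11.0:

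- For every Veteran who starts session 1, adverse events are also ascertained by CPRS review through the date on which the 1-month visit was or would have been due, whether or not the Veteran has left the study. The review covers at least hospital admissions, emergency or crisis contacts and suicide-behaviour reports.
- The review is completed before the links between identifiers and research data are deleted, which section 11.0 schedules for study completion.
- Aim 1 is reported over all who started session 1, with the number not followed to that date.
- Each withdrawal for suicidality, intolerance or acute symptoms is listed in the safety table.

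Confirm that the consent form and HIPAA authorization cover chart review after withdrawal; the form's text was not available for this review, so it may already do so. Also state whether Veterans who stop treatment are still invited to the 1-week and 1-month assessments. The withdrawal and treatment rules stay as they are.

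The cost is about 25 short reviews of a record already accessed, and possibly a line in the consent documents. Care outside the VA would still be missed, and the sponsor should accept that the event count can only rise.
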